### 5.2.8 Missing Task(s) in Questionnaire

If the subject is unable to complete a task within the questionnaire for any cognitive reasons, the worse score for that task should be assigned. If the subject is unable to complete a task due to any of the other non-cognitive opt-out reasons, the score for the respective task should be considered as Missing at Random (MAR). A composite (i.e., total) score can be derived if at least 80% of tasks are not missing with the following formula.

(Sum of Observed Task Scores / Sum of Observed Max Task Scores) \* Sum of All Max Task Scores

QMD Ref: Worldwide-TMP-ST-054-1.0 Effective: 12Aug2022	Governing QMD: Worldwide-SOP-ST-026
Confidentiality Statement	
This document is the property of Worldwide Clinical Trials Inc. and may not be duplicated, copied, altered or removed from company without prior approval from Worldwide Quality Assurance or in compliance with Worldwide Standard Operating Procedures.	

Worldwide Clinical Trials Controlled Quality Management Document		
 WORLDWIDE CLINICAL TRIALS	Sponsor:	EIP Pharma, Inc.
	Protocol Number:	EIP21-NFD-504
STATISTICAL ANALYSIS PLAN		

If more than 20% tasks are missing, then the total score is set to be missing.

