## 5.2.20 Movement Disorder Society – Unified Parkinson’s Disease Rating Scale – Part III (MDS-UPDRS3)

The motor examination (Part III) assesses motor symptoms and signs. The total score is the sum of 33 items with scores ranging from 0-132, with higher scores meaning more severe symptoms. All items have 5 response options ranging from 0 (Normal) to 4 (Severe). Missing data will be handled as defined in section 5.2.8.

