#### **5.10.4.4 Change in MDS-UPDRS3 motor examination (Part III) score**

MDS-UPDRS3 score will be analyzed similar to primary endpoint as described in Section [5.10.2.1](#). Change from baseline will be the dependent variable. The difference in the change from baseline during the double-blind treatment period between the neflamapimod treatment group and placebo with corresponding SE and 2-sided 95% CI will be presented.

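### On MDS-UPDRS Part III, Section 5.2.8 scores a cognitive failure as worst motor impairment, and the SAP does not say how motor inability is recorded

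*SAP*

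**What the plan says.** Section 5.2.20 describes MDS-UPDRS Part III as an examination of motor symptoms and signs. It has 33 items, each scored 0 to 4, and a total from 0 to 132 on which higher is worse. Its only instruction on missing items is "Missing data will be handled as defined in section 5.2.8".

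Section 5.2.8 has two branches. The first is cognitive: "If the subject is unable to complete a task within the questionnaire for any cognitive reasons, the worse score for that task should be assigned". The second covers a task not completed "due to any of the other non-cognitive opt-out reasons, the score for the respective task should be considered as Missing at Random (MAR"). A total is allowed on this condition: "A composite (i.e., total) score can be derived if at least 80% of tasks are not missing". The formula is the ratio "Sum of Observed Task Scores / Sum of Observed Max Task Scores", multiplied by the maximum over all tasks. Beyond that limit, "If more than 20% tasks are missing, then the total score is set to be missing".

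Section 5.10.4.4 then states "MDS-UPDRS3 score will be analyzed similar to primary endpoint", with change from baseline as the dependent variable. Neither Sections 5.2.8, 5.2.20 and 5.10.4.4 nor the post-lock addendum contains an exception for motor items.

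**The concern.** Giving the worst score to a cognitive failure is sensible when the task measures cognition. Part III measures motor function in people with dementia. A subject who cannot follow the instruction for a motor item has shown nothing about the motor sign, yet the rule records it at its most severe grade.

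The second branch raises a conditional problem. Suppose a subject cannot perform an item because of the sign being rated, and the item is entered as not done. That reason is not cognitive, so the item is treated as missing at random and replaced in effect by the subject's own average over the items still performable. Missing at random is hard to defend when the impairment being measured causes the gap.

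At stake is the meaning of the MDS-UPDRS3 estimate and its confidence interval. The descriptive and model tables (14.2.3.3.1a and 14.2.3.3.2) are both marked topline. The OLE analysis approach lists UPDRS Motor (Part III) among the endpoints compared between new and old capsules, with p-values.

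**Working it through.** **Inputs from the SAP.** 33 items, 0 to 4 each, maximum 132 (5.2.20); 80% threshold and proration formula (5.2.8).

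**Input assumed.** The mean score of the observed items, written *m*. The SAP gives none, so a range of 0.5 to 2.0 is used.

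**The plan's own figure.** 33 × 4 = 132, which reproduces.

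**How many items can be prorated.** 0.80 × 33 = 26.4, so 27 items are needed. 27/33 = 81.8% passes and 26/33 = 78.8% fails. At most 6 items can be missing.

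**Formulas, with k items not done.**
- Prorated total = [(33 − k)m / (4(33 − k))] × 132 = 33m, whatever k is.
- Total with those items scored 4 = (33 − k)m + 4k.
- Difference = k(4 − m).

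| Assumed m | Prorated total | Scored 4, k = 1 | Scored 4, k = 3 | Scored 4, k = 6 | Difference (k = 1 / 3 / 6) |
|---|---|---|---|---|---|
| 0.5 | 16.5 | 20.0 | 27.0 | 37.5 | 3.5 / 10.5 / 21.0 |
| 1.0 | 33.0 | 36.0 | 42.0 | 51.0 | 3.0 / 9.0 / 18.0 |
| 1.5 | 49.5 | 52.0 | 57.0 | 64.5 | 2.5 / 7.5 / 15.0 |
| 2.0 | 66.0 | 68.0 | 72.0 | 78.0 | 2.0 / 6.0 / 12.0 |

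**Cognitive branch (follows from the text).** The rule gives the scored-4 total. The last column is the excess over proration, if motor function on the undone items equals the subject's own average. At m = 1, six items add 6 × 4 = 24 points gross. Proration would itself have credited them 33 − 27 = 6 points, so the net excess is 18.

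**Non-cognitive branch (only if motor inability is entered as not done).** The rule gives the prorated total. The same column is then the understatement relative to scoring those items 4.

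**Effect on change from baseline in that conditional case.** Assume a complete baseline total of 33 in which the affected items each score 3. At follow-up those items cannot be performed and all others are unchanged.
- One item (others sum to 30): 30/128 × 132 = 30.9, a change of −2.1. Scored 4, the total is 34, a change of +1.
- Three items (others sum to 24): 24/120 × 132 = 26.4, a change of −6.6. Scored 4, the total is 36, a change of +3.
- Six items (others sum to 15): 15/108 × 132 = 18.3, a change of −14.7. Scored 4, the total is 39, a change of +6.

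A motor decline can therefore be recorded as an improvement.

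**The case against.** A reader might infer that the SAP treats motor inability as missing at random and prorates it away. The document does not establish that. Section 5.2.8 acts only on tasks not completed, and motor inability is not named among the opt-out reasons. If the rater enters 4 for an item the subject physically cannot do, nothing is missing and the rule never applies. Recording instructions may sit in documents not shown here. This objection stands and makes the motor half conditional. It does not touch the cognitive branch, which the SAP states outright.

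A reader might also infer that a cognitive effect of the drug would show up as a motor effect. That requires items to be left undone for cognitive reasons at different rates in the two arms, and the SAP gives no such rates. An item missed for the same reason at baseline and follow-up would also largely cancel in the change score.

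Six items is the ceiling for proration, not an expected case. A subject with several unperformable items may well average above 1 on the rest, which narrows the gap.

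The endpoint's status limits the consequence too. Section 5.10.4 says exploratory endpoints are not tested for significance. MDS-UPDRS3 is outside the hierarchy of Section 5.10.5, and the motor endpoint in that hierarchy is TUG. The OLE text does not say whether Section 5.2.8 governs its UPDRS Motor score.

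**Conclusion.** The concern holds in a limited form. Applying Section 5.2.8 unchanged to Part III assigns worst motor impairment to items missed for cognitive reasons. The excess over proration is 2.0 to 3.5 points for one item and 12 to 21 for six, over assumed mean item scores of 2.0 to 0.5. An understatement of the same size follows for motor inability only if it is recorded as not done, and the SAP leaves that open.

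The effect is confined to the MDS-UPDRS3 estimate and confidence interval, and possibly the OLE UPDRS Motor comparison. The primary result, the testing hierarchy and the sample size are unaffected. Without item-level missingness by arm, neither the direction nor the size of a between-arm bias can be stated. The change should be made, but no confirmatory conclusion depends on it.

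**What to change.** - **Section 5.2.8:** limit the sentence that gives the worst score for cognitive reasons to cognitive tests. Section 5.2.19 also points to 5.2.8 for NPI-12, so check the effect of the new wording there.
- **Section 5.2.20:** replace the bare cross-reference with a rule for Part III. Items not done for cognitive or unrelated reasons are missing, and the total is prorated under the existing 80% threshold. State that inability due to the motor sign being rated is scored by the rater on the 0 to 4 scale and is not handled as missing at random.
- **Documentation:** the addendum states that the study is already unblinded, and Section 5 of the SAP sends post-lock changes to an addendum. Record the change there, report the number of affected items by arm and reason, and show the Part III results under both rules. State which rule the OLE analysis of UPDRS Motor uses.

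The cost is SAP wording, one derivation and a repeat of the Part III tables. The downside is that a few totals will rest on proration, which assumes that the undone items resemble the observed ones.

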### 5.2.9 Exposure to Study Drug

The exposure calculation will take into account interruptions in therapy. The duration of interruption will be subtracted from the total exposure. The exposure to study drug will be calculated as:

(Date of last dose – date of first dose + 1) – (Sum of Interruption durations), where each interruption duration will be calculated as:

End date of treatment interruption – Start date of treatment interruption + 1.

### 5.2.10 Treatment Compliance

Treatment compliance will be calculated per visit as follows:

$$\frac{\text{Total number of capsules dispensed at Visit X} - \text{Total number of capsules returned at Visit Y}}{[\text{Date returned (Visit Y)} - \text{Date dispensed(Visit X)}] \times 3} \times 100$$

Period	Visit Interval	Visit X	Visit Y
Double-Blind Treatment Phase	Baseline to Week 2	Baseline	Week 2
	Week 2 to Week 4	Week 2	Week 4
	Week 4 to Week 8	Week 4	Week 8
	Week 8 to Week 12	Week 8	Week 12
	Week 12 to Week 16	Week 12	Week 16
Open-Label Extension Phase	Week 4 to Week 8	Week 4	Week 8
	Week 8 to Week 16	Week 8	Week 16
	Week 16 to Week 32	Week 16	Week 32

Overall compliance will be calculated as:

$$\frac{\text{Total number of capsules dispensed} - \text{Total number of capsules returned}}{[\text{Date of last dose} - \text{Date of first dose}] \times 3} \times 100$$

Any kits that are not returned will be considered missing data and corresponding treatment compliance will not be calculated.

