## 5.9 Exposure to Study Drug and Treatment Compliance

Extent of exposure (number of days of exposure to study drug), treatment compliance between each scheduled visits and overall compliance will be presented by actual treatment group for the Completer Analysis Set.

Additionally, treatment compliance will be summarized by the following categories:

- <80%
- Within 80-120%
- >120%

All data will be listed.

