**Confidentiality Statement**

This document is the property of Worldwide Clinical Trials Inc. and may not be duplicated, copied, altered or removed from company without prior approval from Worldwide Quality Assurance or in compliance with Worldwide Standard Operating Procedures.

Worldwide Clinical Trials Controlled Quality Management Document			
 WORLDWIDE <small>CLINICAL TRIALS</small>	Sponsor:	EIP Pharma, Inc.	
	Protocol Number:	EIP21-NFD-504	
STATISTICAL ANALYSIS PLAN			

Table Number	Table Title	Validation Method	Shell Number (if repeat)	Topline
	Relationship, Open-Label Extension Phase - Safety Analysis Set			
14.3.1.7a	Treatment-Emergent Adverse Events Leading to Early Withdrawal by System Organ Class, Preferred Term, Double-Blind Treatment Phase - Safety Analysis Set	IP		
14.3.1.7b	Treatment-Emergent Adverse Events Leading to Early Withdrawal by System Organ Class, Preferred Term, Open-Label Extension Phase - Safety Analysis Set	IP	14.3.1.7a	
14.3.2	Listings of Deaths, Other Serious and Significant Adverse Events			
14.3.2.1	Serious Treatment Emergent Adverse Events - Safety Analysis Set	IP		Topline
14.3.2.2	Deaths - Safety Analysis Set	IP		
14.3.3	Narratives of Deaths, Other Serious and Certain Other Significant Adverse Events			
14.3.4	Abnormal Laboratory Values			
14.3.4.1	Abnormal Laboratory Values – Safety Analysis Set	IP		
14.3.5	Extent of Exposure, Dosage Information, And Compliance			
14.3.5.1a	Exposure to Study Drug and Treatment Compliance, Double-Blind Treatment Phase - Completer Analysis Set	IP		
14.3.5.1b	Exposure to Study Drug and Treatment Compliance, Open-Label Extension Phase - Completer Analysis Set	IP	14.3.5.1a	
14.3.6	Vital Signs and Physical Examination			
14.3.6.1a	Vital Signs – Double-Blind Treatment Phase - Safety Analysis Set	IP		
14.3.6.1b	Vital Signs – Open-Label Extension Phase - Safety Analysis Set	IP	14.3.6.1a	
14.3.6.2a	Physical Examination – Double-Blind Treatment Phase - Safety Analysis Set	IP		
14.3.6.2b	Physical Examination – Open-Label Extension Phase - Safety Analysis Set	IP	14.3.6.2a	
14.3.6.3a	Shift Table of Physical Examination – Double-Blind Treatment Phase - Safety Analysis Set	IP		

QMD Ref: Worldwide-TMP-ST-054-1.0_Effective: 12Aug2022	Governing QMD: Worldwide-SOP-ST-026
Confidentiality Statement	

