## **Approach for OLE Analysis**

### **Treatment groups:**

There are five treatment groups in the OLE:

Group 1 = old batch for all of OLE (or through ET), N=20

Group 2 = started OLE on old batch, switched at W16 OLE, N=35

Group 3 = started OLE on old batch, switched at W8 OLE, N=26

Group 4 = started OLE on old batch, switched at W4 OLE, N=22

Group 5 = new batch for all of OLE (or through ET), N=46

Total=149, though not all the participants above will be in the mITT analysis, with some being excluded because they do not have at least one efficacy evaluation during the OLE.

In addition, three populations will be evaluated:

1. All participants in OLE
2. OLE participants with screening plasma ptau181 <25.2 pg/mL (2.2 pg/mL in prior version of assay)
3. OLE participants with screening plasma ptau181 < 21 pg/mL (1.8 pg/mL in prior version of assay)

For OLE week 8 data point, groups 1, 2 and 3 will be pooled under “old capsule treatment” and only group 5 will be included under “new capsule treatment” (i.e. only participants with  $\geq 8$  weeks of new capsules will be included).

For the week 16 OLE analysis, groups 1 and 2 will be pooled under the label of “Old Capsules Treatment”, and groups 3, 4 and 5 will be pooled under the label of “New Capsule Treatment” (i.e. all participants with  $\geq 8$  weeks of new capsules will be included for the new capsule treatment group).

The baseline value for all change analyses will be the value at the end of the double-blind period, i.e. at week 16 of the main study (if no value, week 12 will be carried forward).

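### The OLE compliance intervals in SAP 5.2.10 start at Week 4, so OLE start to Week 4 has no per-interval figure; the overall compliance denominator is also one day short

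*SAP*

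**What the plan says.** Section 5.2.10 defines compliance for each interval as capsules dispensed at Visit X minus capsules returned at Visit Y, divided by three times the days between the two dates. A table then lists the pairs of visits.

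- The double-blind block opens with "Double-Blind Treatment Phase Baseline to Week 2 Baseline Week 2" and continues through Weeks 4, 8, 12 and 16, each interval starting where the last one ended.
- The OLE block opens with "Open-Label Extension Phase Week 4 to Week 8 Week 4 Week 8", continues with Week 8 to Week 16, and closes with "Week 16 to Week 32 Week 16 Week 32".

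A second formula, introduced by "Overall compliance will be calculated as", divides total capsules dispensed minus returned by three times (date of last dose minus date of first dose). Section 5.2.9 counts exposure days as last dose minus first dose plus 1, before subtracting interruptions.

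On reporting, Section 5.9 says that "treatment compliance between each scheduled visits and overall compliance will be presented by actual treatment group for the Completer Analysis Set". Section 10 lists the OLE output as Table 14.3.5.1b, "Exposure to Study Drug and Treatment Compliance, Open-Label Extension Phase - Completer Analysis Set". The post-database-lock addendum adds a rule for a missing last dose date but leaves Section 5.2.10 unchanged.

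**The concern.** The two blocks of the same table are built differently. The double-blind block starts at the first dispensing of drug; the OLE block starts four weeks after it. A programmer following the table would produce Table 14.3.5.1b without an interval that Section 5.9 commits to, and the SAP gives no reason for leaving it out.

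The omitted weeks are of some interest. For subjects randomized to placebo they are the first weeks on active drug, when early tolerability could show up as missed doses. A reader of the OLE table could not see this, because the only figure that includes those weeks averages them with the rest of the phase.

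The denominator is a separate matter of consistency. Two adjacent sections count the same span of days differently, and the compliance version gives a perfectly adherent subject more than 100%.

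**Working it through.** **1. Does an OLE-start-to-Week-4 interval exist?** Four places in the SAP show that it does.

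- Section 5.2.11 separates adverse events by the first dose of study drug in the OLE, so drug is taken from the start of that phase.
- Table 2 in Section 5.2.4 maps OLE Day 2 to Day 33 to a Week 4 visit for vital signs, hematology and chemistry.
- Section 5.2.10 itself uses OLE Week 4 as a Visit X, that is, a dispensing visit.
- The Approach for OLE Analysis describes a group by its switch at that visit: "Group 4 = started OLE on old batch, switched at W4 OLE, N=22".

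A row lost when the PDF was read is unlikely: the OLE phase label sits on the Week 4 to Week 8 row, just as the double-blind label sits on its own first row.

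**2. How much time is uncovered?** The plan states no coverage figure, so this comes from its interval rows.

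| Phase | Intervals listed (weeks) | Weeks covered | Planned weeks | Share covered |
|---|---|---|---|---|
| Double-blind | 0–2, 2–4, 4–8, 8–12, 12–16 | 2 + 2 + 4 + 4 + 4 = 16 | 16 | 100% |
| OLE | 4–8, 8–16, 16–32 | 4 + 8 + 16 = 28 | 32 | 28/32 = 87.5% |

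The uncovered part is 4/32 = 12.5% of planned OLE time, and it is the same four weeks for every OLE participant.

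**3. The overall denominator.** Take a subject who uses three capsules on each of 112 days (16 weeks), first dose on Day 1 and last dose on Day 112.

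- Capsules taken: 112 × 3 = 336.
- Formula in 5.2.10: last minus first = 111 days; 111 × 3 = 333; 336/333 = 1.009, or 100.9%.
- Day count in 5.2.9, with no interruption: 111 + 1 = 112 days; 112 × 3 = 336; 336/336 = 100%.

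The per-interval formula does not share the problem. With visits on their nominal days, the double-blind intervals are 14 + 14 + 28 + 28 + 28 = 112 days and their denominators sum to 336. Only the overall formula is short, so it also disagrees with the interval figures in the same table.

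**4. Effect on the reporting bands.** Section 5.9 groups compliance as below 80%, 80–120% and above 120%. Over 112 days, the stated formula reports 80% when the figure on a 112-day denominator is 80 × 111/112 = 79.3%, and reports 120% when it is 120 × 111/112 = 118.9%. Only subjects within about one percentage point below a cut-off would change band. Over a full 32-week OLE (224 days) the inflation falls to 672/(223 × 3) = 672/669 = 100.4%.

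**The case against.** The best reply is that nothing is lost. Overall compliance covers all drug from first to last dose, Section 5.9 presents it, and Section 10 plans a drug accountability listing. That reply is right as far as it goes, and it rules out a stronger claim a reader might infer, that the first four OLE weeks have no compliance figure at all. It does not answer the narrower point: Section 5.9 commits to figures between visits as well as overall, and a single overall figure cannot show adherence in the first weeks.

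A reader might also infer that the gap distorts the comparison of old with new capsules, since four of the five OLE groups spent those weeks on old capsules. The document does not support that.

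- Every participant loses the same four weeks, including those on new capsules throughout.
- In the planned Week 8 comparison (Groups 1–3 against Group 5), 4 of 8 weeks have interval compliance on both sides.
- Section 5.9 shows compliance by actual treatment group, and Section 5.3 keeps subjects in their double-blind group during the OLE. No planned table splits compliance by batch.
- The OLE approach does not use compliance as a covariate, a population rule or a sensitivity analysis.
- Group 4, whose old-capsule period falls wholly in the gap, is left out of the Week 8 efficacy comparison and counted as new-capsule treatment at Week 16.

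On the denominator, it is fair to say that 0.9 percentage points is minor against bands 40 points wide. That stands as a comment on size; the inconsistency with Section 5.2.9 remains.

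**Conclusion.** The point holds as a minor correction. Section 5.2.10 omits a per-interval figure for OLE start to OLE Week 4, 4 of 32 planned OLE weeks, against its own double-blind pattern and the commitment in Section 5.9. Independently, the overall formula overstates full adherence by 0.9 percentage points over 112 days. Neither defect touches the primary or secondary efficacy analyses, and neither biases a specified OLE comparison.

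The 12.5% is planned time under the visit schedule implied by the SAP, not observed exposure. The 100.9% assumes three capsules on every day from first to last dose, including both end days, and no interruption. Compliance is tabulated for completers only, so double-blind durations should be close to 112 days and the inflation close to 0.9 points.

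**What to change.** 1. Add an OLE row to the interval table in Section 5.2.10, with Visit X the OLE-start dispensing visit and Visit Y OLE Week 4. If the interval was left out on purpose, say why and reword Section 5.9 to match.
2. Change the overall denominator to (date of last dose − date of first dose + 1) × 3, matching the day count in Section 5.2.9. Leave the per-interval denominator as it is.

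The cost is one table row, one term in a formula and a rerun of Tables 14.3.5.1a and 14.3.5.1b. This assumes that returned capsules were counted at OLE Week 4. The double-blind rows use each intermediate visit for both return and dispensing, but the SAP does not describe the OLE return schedule, so check it against the accountability data. As the database is locked, the change belongs in a further post-lock addendum, as Section 5 requires.

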### 5.2.11 Adverse Events

A treatment-emergent Adverse Event (TEAE) is defined as one that started, or worsened in severity or seriousness, following the first dose of study drug. An AE with onset prior to the start of administration of the first dose of study drug, or when the stop date is before the start of the administration of the first dose of study drug, or when the study drug was not started, will be considered as pre study. In case the onset date is on the same day as the first dose of study drug

QMD Ref: Worldwide-TMP-ST-054-1.0_Effective: 12Aug2022	Governing QMD: Worldwide-SOP-ST-026
Confidentiality Statement	
This document is the property of Worldwide Clinical Trials Inc. and may not be duplicated, copied, altered or removed from company without prior approval from Worldwide Quality Assurance or in compliance with Worldwide Standard Operating Procedures.	

Worldwide Clinical Trials Controlled Quality Management Document		
 WORLDWIDE CLINICAL TRIALS	Sponsor:	EIP Pharma, Inc.
	Protocol Number:	EIP21-NFD-504
STATISTICAL ANALYSIS PLAN		

and either the time of first dose or time of AE onset is missing, then AE is considered treatment-emergent.

TEAEs starting after first dose of study drug in the double-blind treatment phase and before the first dose of study drug in the open-label extension phase will be summarized under the Double-Blind summary. TEAEs starting after first dose of study drug in open-label extension phase will be summarized under the open-label extension phase.

Maximum severity (Severe) will be assumed for an AE with missing severity.

A treatment-related AE is defined as an AE as being possibly related or related to the study drug. If an AE has missing relationship it is assumed to be related to the study drug for analysis purposes.

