### 5.12.1 Adverse Events

The following tables will be presented for AEs. Incidence and/or number of events will be reported as appropriate:

- Overall summary of TEAEs
- TEAEs by system organ class and preferred term
- Treatment related TEAE by system organ class and preferred term
- Serious TEAE by system organ class and preferred term
- TEAE by system organ class, preferred term and maximum severity
- TEAE by system organ class, preferred term and closest relationship
- TEAEs leading to early withdrawal by system organ class and preferred term
- Listing of Serious TEAEs (presented in the Table section of the appendices).
- Listing of Deaths (presented in the Table section of the appendices).

AE incidence is counted only once per system organ class and once per preferred term. The number and percent of subjects experiencing events are reported. Outputs reported at maximum severity show the highest severity reported by a subject per system organ class and preferred term. MedDRA version 26.1 or higher will be used for coding purposes.

All AEs will be listed.

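### Section 5.2.11 classes an AE that begins before first dose and worsens after it as both treatment-emergent and pre-study, and gives it no phase, so it could be missing from the TEAE tables

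*SAP*

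**What the plan says.** Three rules in SAP Section 5.2.11 bear on this point.

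- **TEAE definition.** A TEAE is "one that started, or worsened in severity or seriousness, following the first dose of study drug". Starting and worsening are alternatives, and either is enough.
- **Pre-study definition.** The next sentence begins "An AE with onset prior to the start of administration of the first dose of study drug", adds events that stopped before first dose, and ends "or when the study drug was not started, will be considered as pre study". The three conditions are joined by *or*, so early onset alone is enough.
- **Phase allocation.** The double-blind summary takes "TEAEs starting after first dose of study drug in the double-blind treatment phase", up to the first open-label dose. For the extension, "TEAEs starting after first dose of study drug in open-label extension phase will be summarized under the open-label extension phase". Neither clause mentions worsening.

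Section 5.12.1 builds the AE tables on the TEAE class, for example "TEAEs by system organ class and preferred term", and the list of tables in Section 10 splits them by phase (14.3.1.1a/b to 14.3.1.7a/b). Section 5.12.1 also states: "All AEs will be listed".

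**The concern.** The two definitions give opposite answers for one kind of event: an AE that begins before first dose, is still present afterwards, and then becomes more severe or serious. The TEAE definition is worded to include it and the pre-study sentence excludes it.

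At stake is the count of on-treatment safety events. The TEAE class feeds the overall summary and the tables by system organ class and preferred term, relatedness, seriousness, maximum severity, relationship and early withdrawal. The serious-event listing placed among the tables (14.3.2.1) is also limited to treatment-emergent events. An AE that was mild at screening and became serious on drug could be absent from all of these.

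That would go against the rest of the section, which resolves doubt conservatively. Missing severity is taken as severe, missing relationship as related, and an onset on the day of first dose with a missing time as treatment-emergent.

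**Working it through.** The plan states no figure here and no arithmetic applies. The check takes one test event through each rule.

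**Test event.** Onset between consent and first dose; not resolved at first dose; severity or seriousness increases after first dose; the worsening is entered on the original AE record, so the onset date stays before first dose.

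1. **TEAE definition.** The event did not start after first dose, but it worsened after it. Result: TEAE.
2. **Pre-study definition.** Onset is before first dose and that condition is sufficient. The other two conditions are not met, since the event had not stopped and drug was started. Result: pre-study.
3. **Double-blind allocation.** The event did not start after the first double-blind dose. Result: not in the double-blind summary.
4. **Open-label allocation.** The event did not start after the first open-label dose. Result: not in the open-label summary.

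Steps 1 and 2 conflict. Steps 3 and 4 leave the event without a phase even if step 1 prevails.

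**What the worsening condition is for.** An AE that starts after first dose is already a TEAE by its start. Worsening therefore adds only events that began before first dose, and the pre-study sentence removes exactly those. Read literally, it leaves the worsening condition with no effect.

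**Whether another rule resolves it.** None does.

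- Section 5.2.7.1 imputes missing and partial dates; it does not deal with worsening.
- The same-day rule in Section 5.2.11, and the matching exception in Section 5.2.3, deal with missing times.
- The post-lock addendum changes the efficacy model, adds a rule for a missing last-dose date and adds pTau181 tables. It does not touch Section 5.2.11.

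**How the outcome depends on recording and reading.**

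| How worsening is recorded | Rule followed | Event in the phase-specific TEAE tables? |
|---|---|---|
| New AE record, onset after first dose | Any | Yes; all rules agree |
| Original record, onset before first dose | Pre-study sentence | No |
| Original record, onset before first dose | TEAE definition, phase by start as written | Flagged as a TEAE, but in neither phase summary |
| Original record, onset before first dose | TEAE definition, phase by date of worsening | Yes, but this phase rule is not in the SAP |

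**The case against.** The strongest reply is that this is an ambiguity and not a demonstrated loss. The TEAE sentence is the formal definition and names worsening, so a programmer could let it govern. How worsening is recorded is normally fixed by the protocol or the CRF instructions, which are not shown; if it opens a new record, nothing is lost. Affected events also remain visible in the AE listing (16.2.7.1) and, where relevant, in the listing of AEs leading to early withdrawal (16.2.7.2). All of this stands, and it makes the loss conditional. It does not remove the contradiction, because giving the TEAE sentence precedence still leaves the event without a phase.

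Three stronger readings are tempting, and the SAP does not support them.

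- *A reader might infer that worsened events certainly drop out of the tables.* That depends on the recording practice and on which sentence is followed, and the SAP settles neither.
- *A reader might infer that an AE starting in the double-blind phase and worsening in the extension is also lost.* It is not. It is a TEAE by its start and is counted once, in the double-blind summary. Allocation by starting phase is a usable convention for such events.
- *A reader might infer that aggravation of existing symptoms is a main route of harm in this population, so that many events are affected.* Nothing in the SAP says so. Section 5.7 tabulates ongoing conditions as medical history. If one of these worsens and is then reported as an AE, it may well carry a post-dose onset. The exposed set may be limited to AEs arising between consent and first dose.

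**Conclusion.** The contradiction is in the current text and nothing else in the SAP resolves it. For an AE with onset before first dose that worsens afterwards, Section 5.2.11 gives two incompatible classes and no phase.

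The effect on the tables is conditional. It arises if worsening is kept on the original AE record and either the pre-study sentence or the start-based phase rule is applied as written. Such events would then be missing from the TEAE tables by phase, while remaining in the full AE listing. With a new record at worsening, none is missing. Because the SAP gives neither AE counts nor the recording rule, the size can only be bounded, from none to all of such events. This is a minor point that is worth correcting because the rules as written can produce a wrong safety count.

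**What to change.** Make two changes to Section 5.2.11.

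1. Reword the pre-study sentence so that an AE with onset before first dose is pre-study only if it did not worsen in severity or seriousness after first dose.
2. Add that a pre-dose-onset AE that worsened is allocated once, to the phase in which it first worsened. Leave AEs that start after first dose allocated by start date.

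Simply adding worsening to both phase rules would be the wrong repair. An AE that starts in the double-blind phase and worsens in the extension would then enter both summaries, with no rule for which severity counts in each.

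The cost is small but not nil. The addendum states that the study has been locked and unblinded, so under Section 5 the change belongs in a post-database-lock addendum. The sponsor should state which rule was applied, check AEs with onset before first dose for later worsening, and re-run the affected tables if any worsened. The allocation rule needs the phase of first worsening to be identifiable. The SAP does not show that a date of worsening is collected, so the addendum should name the data used.
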